07-RAD-01-UK/P4:
Stereotactic Body Radiation Therapy for Post-chemoradiation
Residual Disease in Stage II/III Non-small Cell Lung Cancer

Principle Investigator:

[name]., Ph.D.
Department of Radiation Medicine
University of Kentucky

Medical Oncology Co-Investigators:

[name].
[name].
Department of Hematology/Oncology,
University of Kentucky

Imaging Co-Investigators:

[name].
[name].
Department of Diagnostic Radiology,
University of Kentucky

Statistical Co-Investigator:

[figure not shown]
[name].
Departments of Internal Medicine & Biostatistics
University of Kentucky Colleges of Medicine & Public Health

Study version 1.5.2 July 8, 2013

SCHEMA

Eligible patients with Stage II/III NSCLC[#]

Completed Definitive Chemoradiation to min 5940 cGy*

[figure not shown]

CT scan or PET/CT 21-30 days post chemo RT

SBRT boost

Peripheral Tumors: 1000cGy X 2 to residual primary mass

Medial Tumors: 650cGy x 3 to residual primary mass

Routine Followup with CT chest and/or chest x-ray at ~3 months

PET/CT if suspected recurrence/metastasis clinically indicated

Sample size: 42 patients

1.0 Background

Lung cancer represents one of the most challenging malignancies to manage. Cure rates have only marginally improved in the last 20 years. It is the most commonly fatal cancer in both men and women with overall 5 year survivals of 15%. Lung cancer kills more Americans than the next three most common malignancies combined.

Most non small cell lung cancer (NSCLC) presents at advanced stages. Only approximately 25% present with stage I/II disease, 40% with stage III and 35% pts present with stage IV. (1) The optimal treatment of stage II/III NSCLC is complex. For those patients who are surgical candidates and a complete resection is technically feasible, radical surgery remains the standard of care. Traditionally, those patients with multiple N2 nodal levels or T4 disease are considered inoperable. Given that the average age of patients diagnosed with NSCLC is in their mid-60's and usually have long smoking histories, many patients are medically inoperable.

1.1 Current Radiation Therapy for NSCLC

In the early 1980's, the CALGB completed a protocol for the treatment of stage III NSCLC that employed chemotherapy first, which they called "proto-adjuvant." They based the treatment on two cycles of cis-platinum and 4 weekly doses of vinorelbine – no alkylating agents. This landmark, paradigm shifting trial widely known as the Dillman trial (2) altered the course of non-surgical therapy by demonstrating that treatment regimens including chemotherapy were significantly better than radiotherapy alone. The median survival was nearly 14 months with the chemotherapy and only in the range of 9 months with radiotherapy alone to 60 Gy (2). The study was replicated by an Intergroup effort (3). The theory and apparent fact was that these tactics reduced distant metastasis, but did not alter local control and failure in the chest remains a significant problem in the management of NSCLC(3).

1.2 Radiation Therapy – What dose to use.

The optimal doses of radiation therapy are undefined but the high local failure rates (vary between 20 and 50%) would suggest that higher doses of radiation therapy could potentially improve outcome in these patients. Local failure results in significant morbidity and theoretically could act as a nidus for metastasis. While various dose

escalation trials are beginning to suggest a benefit to increasing the RT dose to obtain better local control, thus far no prospective trials have shown benefit to escalation of the most common RT dose, 60Gy, established in the Dillman trial (2), probably due to the limitations of dose imposed by patient anatomy. Tolerance of organs such as esophagus, spinal cord and heart are important, but the lungs themselves are of primary importance with a dose limiting toxicity being pneumonitis. Pneumonitis has a dose volume relationship which is not clearly definable due to the variability in lung physiology (e.g. emphysematous bullae, upper vs. lower lobes) and attempts to develop predictive models for pneumonitis are fraught with difficulties. We often examine the so-called V_{20} value, basically the volume of lung encompassed by the 20Gy isodose line in patients receiving standard fractionation (180-200 cGy/fraction)(4).

Most studies of dose escalation have included patients with high stage disease. Due to the high risk of local recurrence, several studies have undertaken dose escalation using different strategies to maintain toxicity at acceptable levels. Most strategies try to equate dose/fractionation schemes by employing linear quadratic normalization (biological effective doses (BED)). This is somewhat difficult since it does not take into account the lengths of treatment time in hypofractionated schemes. Applying the linear quadratic equation ($BED=nd(1+d/\alpha/\beta)$ where n=the number of fractions, d=the dose/fraction and α/β ratio of 10 for acute reacting tissue and tumor cells), 70 Gy will only have a BED of approximately 84 Gy. Using a mathematical model, Martel et al. (5) predicted that for NSCLC patients, the dose to achieve significant probability of tumor control may be at least 84 Gy (100 Gy BED at 200 cGy/fraction) for longer (>30 months) local progression-free survival. RTOG 9311 was a multi-institutional trial in which a total of 179 patients were enrolled in a Phase I-II three-dimensional radiotherapy dose-escalation fashion (6). Patients were stratified at escalating radiation dose levels depending on the percentage of the total lung volume that received >20 Gy with the treatment plan ($V(20)$). Patients with a $V(20) < 25\%$ (Group 1) received 70.9 Gy in 33 fractions, 77.4 Gy in 36 fractions, 83.8 Gy in 39 fractions, and 90.3 Gy in 42 fractions, successively. Patients with a $V(20)$ of 25-36% (Group 2) received doses of 70.9 Gy and 77.4 Gy, successively. $V(20)$ has been used as an indicator of risk for pneumonitis (see below). The radiation dose was safely escalated using three-dimensional conformal

techniques to 83.8 Gy for patients with V(20) values of <25% (Group 1) and to 77.4 Gy for patients with V(20) values between 25% and 36% (Group 2), using fraction sizes of 2.15 Gy. The 90.3-Gy dose level was too toxic, resulting in dose-related deaths in 2 patients. Elective nodal failure occurred in <10% of patients. This study showed that for patients receiving RT alone or radiation following induction chemotherapy, doses of 83.8 Gy using 3-dimensional conformal RT techniques were tolerable, with excess mortality observed at 90.3 Gy. On a theoretical basis when converted to BED, this represents a borderline dose of RT to gain a high probability of local control, especially considering that patients entered on these trials were highly selected.

Since the advent of concurrent chemotherapy and 3-dimensional conformal RT the maximum tolerated dose of radiation has been reduced, and current indications suggest that the maximum tolerated dose in this setting is in the range of 70 to 74 Gy (4,6). Nonetheless, it has not been prospectively demonstrated that dose escalation has produced superior outcomes and careful planning is needed to avoid toxicities. Willner et al. (7) retrospectively examined the influence of total dose and tumor volumes on local control and survival in primary radiotherapy of non-small cell lung cancer. They concluded that there is a dose effect on local control and survival with doses of at least 70 Gy (standard fractionation) and that tumors with volumes $\geq 100\text{cc}$ may require higher doses.

It thus stands to reason that improved local control may result from higher local radiation doses and hypofractionated stereotactically delivered radiation therapy is proving effective at long term control of early stage NSCL (8-10). In an analysis of various hypofractionated stereotactic-delivered radiation schemes, Wulf et al. (11) reports that for an optimal control of a stage one lung cancer, a BED of $>100\text{Gy}$ is required in agreement with the Martel analysis. Moreover as tumors get larger, with greater central hypoxia and numbers of cancer cells to kill, the amount of radiation needed to sterilize a given cancer should theoretically be higher.

1.3 Hypothesis

In light of the above information, it becomes apparent that local control for NSCLC remains a significant problem. Conventional radiation therapy techniques have limitations for the dose that can be delivered to a chest tumor mass due to the adjacent

dose limiting organs. Mounting evidence supports the use of hypofractionated stereotactically delivered radiation therapy to control lung cancer with acceptable toxicity profiles.

Thus we propose to increase the doses of radiation to residual masses of NSCL to a BED >100 Gy by the addition of 2-3 fractions of stereotactically delivered boost radiation therapy to residual disease post-conventional chemoradiation to at least 59.4 Gy in 180 cGy fractions. Using the linear quadratic equation to model doses of radiation therapy, 59.4 Gy would have a BED of approximately 70 Gy. Single fraction stereotactic body radiation therapy (SBRT) of 10 Gy would have a BED of approximately 20 Gy. Thus the addition of two fractions of 10Gy of SBRT to limited volumes of PET residual disease would theoretically result in higher degrees of local control of lung cancer masses, achieving a minimum cumulative BED of approximately 110Gy-equivalent.

2.0 Objectives

Primary

1. to determine the toxicity of the SBRT boost dose by estimating the proportion of subjects enrolled who develop pneumonitis

Secondary

1. to determine response rates of the residual primary tumor following SBRT boost

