7.0 Patient assessments

Assessments	Pre-Study entry ^a	1mo ^f Post SBRT	3mo ^f Post SBRT	Follow Up ^g	As Indicated
History/physical	X	X	X	X	
Pregnancy test ^b	X				
Toxicity eval ^c		X	X	X ^c	
PET-CT	X				X
CXray/CT		X ^d	X ^d	X ^d	X
PFT's ^e	X	X	X		X
CMP/CBC	X				

- a. Pre-study evaluations typically done 3-4 weeks after completion of primary chemoradiation. CT simm typically done approximately 1 week following study entry, with SBRT delivery done approximately 1 week after CT simm.
- b. Pregnancy test if indicated and not done prior to chemo-RT
- c. Toxicity evaluation through 6 months
- d. Ideally alternate CT/Chest rays on routine visits post-treatment
- e. Pulmonary function tests to include spirometry, lung volumes and diffusion capacity
- f. Approximate timeframe
- g. Routine follow-up visits scheduled as per institutional standard (strict FU scheduled not required).

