8.2 Baseline documentation of Target and Non-target lesions

The longest diameter (LD) for the target lesion will be calculated from the treatment planning CT scan using pulmonary windowing and reported as the baseline LD. The baseline LD will be used as the reference by which to characterize the objective tumor response. For follow-up assessment, diagnostic CT scans using lung windows are the preferred modality. Local treatment effects in the vicinity of the tumor target may make determination of tumor dimensions difficult e.g. patchy consolidation.

All other lesions which appear or enlarge after treatment e.g. regional lymph nodes and distant metastases should be identified as non-target lesions and should be recorded at the time of their appearance/suspicious enlargement. Patients who have suspicious CT scans may have PET/CT to assess local failure/distant metastasis as per clinical judgment.

8.2.1. Post treatment followup - Followup evaluation will be performed approximately 30 days after completion of all protocol treatment to assess toxicity and tumor response.

Follow-up for evaluation of toxicity will continue for 6 months following SBRT delivery. Additional follow-up for local control and survival will continue until death or study withdrawal.

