10.0 Statistical Considerations

10.1. Sample size justification :

In this pilot protocol, it is anticipated that 37 patients will be enrolled to receive boost therapy. This number of patients will provide a 10% level of precision (half-width of a 90% confidence interval) for the true (unknown) proportion of subjects that will experience toxicity-limiting pneumonitis. The investigators believe this proportion will be no greater than 20% and have used this number in the sample size justification based on the 90% confidence interval width.

10.2 Stopping rules for severe pneumonitis:

We anticipate that pneumonitis may be the most common radiation-related side effect, and patients will be closely monitored for development of severe pneumonitis in this study. An historical rate of severe pneumonitis rate has been documented to be as high as 15% but varies depending on the volume of lung being irradiated (12). Treatment of most stage III lung cancers carry risks in the 15% and higher range due to volumes of lung irradiated. As such, the protocol will be stopped if sufficient evidence exists suggesting that, among patients receiving therapy, the true incidence of severe pneumonitis exceeds 15%. Sufficient evidence will be statistically defined in the form of an estimate for the severe pneumonitis rate (binomial proportion) whose lower 90% confidence limit exceeds 15%, and these estimates will be made after every 5th enrolled patient to the study. Operationally, any of the following observed ratios (# experiencing severe

pneumonitis of total number observed) would lead to exceeding such a limit: 3 or more of the first 5; 4 or more of the first 10; 5 or more of the first 15; and 6 or more of the first 20.

If the true probability of severe pneumonitis incidence is 10%, the probability of stopping the study under these rules is less than 1% after enrollment of 5 patients on the study, <1.3% after enrollment of the first 10, and roughly <1% after enrollment of 20 patients on the study. If the true probability is 20%, then the probability of stopping after 5, 10, and 20 patients is 6%, 12% and 19%, respectively. If the true probability is 40%, the probability of stopping after 5, 10, and 20 patients is approximately 32%, 62%, and 88%, respectively.

11. Reporting Toxicity

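### Ungraded pneumonitis among all enrolled subjects is the primary measure, but the precision and the stopping rule refer to other undefined events, and the 10-point half-width does not hold at the plan's own 20%

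*Combined protocol and SAP*

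**What the plan says.** - **Section 2.0, primary objective.** Toxicity of the boost is to be determined "by estimating the proportion of subjects enrolled who develop pneumonitis". No grade is given, and the denominator is everyone enrolled.
- **Section 10.1, sample size.** The quantity estimated is the "proportion of subjects that will experience toxicity-limiting pneumonitis", which the investigators put at 20% at most. The planned number is 37, and "This number of patients will provide a 10% level of precision (half-width of a 90% confidence interval". The schema gives a different number: "Sample size: 42 patients".
- **Section 10.2, stopping rule.** The trial stops on sufficient evidence that, "among patients receiving therapy, the true incidence of severe pneumonitis exceeds 15" per cent. On timing, "these estimates will be made after every 5th enrolled patient to the study". The boundaries are 3 of 5, 4 of 10, 5 of 15 and 6 of 20.
- **Section 11.** Acute and late effects are recorded on CTCAE v3.0. The only numeric grades are 4 and 5, which trigger expedited reporting of any radiation-attributable toxicity.
- **Section 7.0, footnote a.** "CT simm typically done approximately 1 week following study entry, with SBRT delivery done approximately 1 week after CT simm".
- **Section 8.2.1.** "Follow-up for evaluation of toxicity will continue for 6 months following SBRT delivery".

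**The concern.** The trial has one primary quantity, a pneumonitis rate, and one statistical stopping rule, also on pneumonitis. The event has three names across the sections that define, size and monitor it, and none of them has a grade. Two analysts with the same graded data could report different primary rates and each cite the protocol. At the monitoring looks, whether the trial stops can turn on how one patient is classified.

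The denominator also shifts between sections. The aim is the toxicity of the boost, and a subject who enrols but never receives it cannot have boost toxicity, so counting that subject lowers the rate. Finally, the precision statement that supports the sample size should be reproducible from its own inputs.

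**Working it through.** **1. The stated precision.** Inputs from section 10.1: rate p = 0.20, 90% two-sided interval (z = 1.6449, z² = 2.7055), half-width 0.10, n = 37. From the schema: n = 42.

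Half-width = z × √(p(1 − p)/n):
- n = 37: 1.6449 × √(0.16/37) = 0.108
- n = 42: 1.6449 × √(0.16/42) = 0.102
- n = 44: 1.6449 × √(0.16/44) = 0.099

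Required n = z² p(1 − p)/0.10² = 2.7055 × 0.16/0.01 = 43.3, so 44.

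The stated 37 is not reproduced. Other 90% intervals do not rescue it: the smallest n is 43 for Wilson and Jeffreys, 44 for Agresti–Coull and 52 for Clopper–Pearson. At n = 37 the half-width is 10.6 points by Wilson and 11.9 by Clopper–Pearson. With 42, Wilson and Jeffreys come to 10.0, so there the shortfall is negligible. The formula gives 37 at a rate of 16% (2.7055 × 0.16 × 0.84/0.01 = 36.4), which the plan does not use.

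**2. The event, section by section.**

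| Section | Event | Grade | Rate attached | Counted among |
|---|---|---|---|---|
| 2.0 | pneumonitis | none | none | enrolled subjects |
| 10.1 | toxicity-limiting pneumonitis | none | at most 20% | subjects (37 to be enrolled for boost) |
| 10.2 | severe pneumonitis | none | 15% | treated patients; looks set by enrolment |

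Sections 5.3.1 and 5.3.4 use two further terms, high-grade acute and clinical pneumonitis, again without a grade. Section 5.3.1 treats the incidence and the severity of pneumonitis as separate things, so the two cannot be assumed to be interchangeable in section 2.0.

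**3. How much one classification matters at a look.** The boundaries reproduce as one-sided 90% exact (Clopper–Pearson) lower limits, the 10th percentile of Beta(x, n − x + 1), compared with 15%:

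| Look | Boundary count: lower limit | One fewer: lower limit |
|---|---|---|
| 5 | 3: 24.7% | 2: 11.2% |
| 10 | 4: 18.8% | 3: 11.6% |
| 15 | 5: 17.2% | 4: 12.2% |
| 20 | 6: 16.6% | 5: 12.7% |

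The arithmetic of the boundaries is sound. At every look, moving one patient across the grade line can carry the limit over 15% or back. The plan's own operating figures show the sensitivity: after 20 patients, the stopping probability is roughly 1% if the counted event has a true rate of 10%, and 19% if it is 20%. The documents do not tie either rate to a grade, so this shows the direction only.

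**4. Denominator.** SBRT comes about two weeks after entry (one week to simulation, one more to delivery), so an enrolled subject can leave before treatment. The documents give no number. Assuming a fraction u is untreated and has no boost pneumonitis, the rate among enrolled subjects = rate among treated × (1 − u):
- u = 5%: 0.20 × 0.95 = 19.0%
- u = 10%: 0.20 × 0.90 = 18.0%

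**The case against.** The best defence is that section 10.1 is meant to specify section 2.0, and that CTCAE v3.0 is adopted for all side effects, so grades will exist. That may be the intent, but no sentence says so, and recording grades does not choose a cut-off. It does limit the claim: CTCAE v3.0 may itself attach a meaning to severe, and that document is not at hand. What can be said is that the protocol text states no cut-off, not that the rule is impossible to apply.

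On the denominator, section 10.1 says patients are enrolled in order to receive the boost, entry follows completed chemoradiation, and section 10.2 already names treated patients as its population. Enrolled and treated should nearly coincide. This stands: the effect is probably small, and shifts of 1 to 2 points are well inside a half-width of about 10.

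Stronger readings are tempting, and the documents do not support them:
- **That 42 are enrolled and 37 treated.** The 37 in section 10.1 is itself an enrolment figure, and nothing says five subjects go untreated. The two numbers conflict; they do not measure dilution.
- **That the precision shortfall comes from the undefined terms, or disappears if the rate is 15%.** Section 10.1 attaches 20% to its own named event, and the shortfall exists at that rate however the event is defined. The 15% is a historical rate and stopping threshold, not a planning rate.
- **That precision for any-grade pneumonitis is far worse than stated.** The documents give no any-grade rate, so no figure can be claimed.
- **That the plan leaves open which events the 20% and 15% describe.** Section 10 assigns each to a named event; only the grades and the link to section 2.0 are missing.

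**Conclusion.** The point holds in three parts of unequal weight.

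The main part is textual and certain: the primary, sizing and stopping events are neither linked nor graded. The stated precision therefore cannot be attached to the primary rate as written, and the stopping counts depend on an unstated cut. A stopping rule may properly use a different event from the primary one, provided that it is defined.

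The second part is arithmetic. At the plan's own 20%, the 90% half-width is 10.8 points with 37 patients and 10.2 with 42, not 10; 44 would be needed. These are normal-approximation figures. The excess is 0.8 or 0.2 points, so the statement needs correcting but the design is not undermined.

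The third part, the enrolled denominator, is minor and of unknown size. The 19% to 18% range rests wholly on an assumed 5% to 10% untreated.

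**What to change.** 1. Reconcile sections 2.0 and 10.1 to one pneumonitis event with a CTCAE v3.0 cut-off chosen by the investigators, counted within the existing six-month window after SBRT. Fix it before outcome data are reviewed; in an open single-arm study, a later choice could be steered by the events seen.
2. State in section 10.2 the cut-off meant by severe, which may differ from the primary one. Fix it before the first look at five patients.
3. Use patients who receive at least one SBRT fraction as the denominator for the primary rate, and for both the counts and the timing of the stopping looks. Report all-enrolled and any-grade rates descriptively.
4. Settle the sample size (37 or 42) and restate the half-width for the chosen event. If 20% is kept, it is 10.8 points at 37 or 10.2 at 42.

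The cost is wording in sections 2.0, 10.1 and 10.2, a slightly less favourable precision statement and one descriptive table. Data collection does not change, since toxicity is already documented on CTCAE v3.0 for six months. Counting looks by treated patients delays each look slightly relative to enrolment.

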11.0 All patients will be assessable for toxicity, and those with measurable disease will be assessable for response. All grade 4 or grade 5 toxicities that are attributable to radiation therapy will be reported to the DSMB and Institutional Review Board within 24 hours of discovery. The boost therapy is given in a two to three day period, and definitions of acute vs. late effects are used as below. Monitoring of late effects of radiation therapy (most commonly pneumonitis) will continue for 6 months following completion of the boost therapy.

11.1 *Acute Radiation Toxicity Monitoring:* Acute (\leq 90 days from RT start) side effects of radiation therapy will be documented using the NCI Common Toxicity Criteria version 3.0. A copy of the CTCAE version 3.0 can be downloaded from the CTEP homepage (<http://ctep.info.nih.gov>).

11.2 *Late Radiation Toxicity Monitoring:* Late ($>$ 90 days from RT start) side effects will be documented using the NCI Common Toxicity Criteria version 3.0.

11.3 Death from any cause while the patient is receiving protocol treatment and up to 30 days after the last protocol treatment, will be reported directly to the DSMB and IRB

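### The primary pneumonitis rate is a crude proportion with no rule for living patients whose toxicity assessment stops before month 6, so as written it is biased slightly downward

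*Combined protocol and SAP*

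**What the plan says.** The primary objective in section 2.0 is to determine toxicity by "estimating the proportion of subjects enrolled who develop pneumonitis". That line gives no time window and no rule for incomplete observation.

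Section 10.1 sizes the trial on the confidence interval of a simple proportion: "it is anticipated that 37 patients will be enrolled to receive boost therapy", for a "10% level of precision (half-width of a 90% confidence interval", with an assumed proportion of at most 20%.

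Section 11.0 opens with "All patients will be assessable for toxicity" and asks for no minimum observation. The window comes from section 8.2.1: "Follow-up for evaluation of toxicity will continue for 6 months following SBRT delivery". In the section 7.0 table, only the 1-month and 3-month visits after SBRT are named. Toxicity evaluation then continues at routine visits through month 6, on the institution's usual timetable, and the table notes say a strict schedule is not needed.

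Section 12.0 removes patients for noncompliance or withdrawal of consent and does not say how their pneumonitis status then enters the estimate. Section 11.3 requires deaths up to 30 days after treatment to be reported, and section 8.2.1 continues survival follow-up. Neither links deaths to the pneumonitis rate. The plan contains no censoring rule, evaluability rule, competing-risk method or sensitivity analysis for the primary estimate.

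**The concern.** A crude proportion estimates the 6-month incidence correctly only if every patient is observed until pneumonitis, death or month 6. The second half of the window has no required visit, and patients can leave the study alive. Pneumonitis that arises after the last evaluation is not seen, but the patient still counts in the denominator. The error has one direction, toward a lower rate. Enrolling more patients does not remove it, and the confidence interval does not reflect it.

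Death raises a different issue. A patient who dies at month 2 without pneumonitis truly did not develop it, so the count is right. But a low rate then has two possible readings: the boost is well tolerated, or patients died before pneumonitis could appear. A reader needs the death figure next to the pneumonitis figure to tell these apart.

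This is the trial's primary question, and the plan's own reference values of 15% (section 10.2) and 20% (section 10.1) are only 5 points apart.

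**Working it through.** **1. The plan's own precision figure.** The inputs from section 10.1 are p = 0.20, a two-sided 90% interval (z = 1.645) and N = 37.

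- Wald half-width = 1.645 × √(0.20 × 0.80 / 37) = 0.108, or 10.8 points.
- The N needed for exactly 10 points is 1.645² × 0.16 / 0.10² = 43.3, so 44.

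The stated 10 points is therefore not quite reached at 37. The schema gives "Sample size: 42 patients", for which the half-width is 10.2 points. The two sample sizes need reconciling, but that is a separate matter. The yardstick used here is about 11 points.

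**2. Inputs for the size of the bias.** The documents give no rate of early death or of lost assessment in this trial, so these are assumptions:

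- Death: exponential with a 14-month median, borrowed from the historical trial in section 1.1 ("The median survival was nearly 14 months with the chemotherapy"). Hazard d = ln 2 / 14 = 0.04951 per month.
- Pneumonitis: 6-month risk of 20% in patients who remain alive, constant hazard. a = −ln(0.80)/6 = 0.03719.
- Loss to assessment while alive: L = 0, 10% or 20% by month 6, constant hazard. c = −ln(1 − L)/6 = 0, 0.01756 or 0.03719.
- The three processes are independent.

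**3. What the crude proportion is expected to read.** Let s = a + d + c. The expected value is (a/s) × (1 − exp(−6s)).

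| Loss L | s | Crude proportion | Bias from loss |
|---|---|---|---|
| 0 | 0.08670 | 17.4% | none |
| 10% | 0.10426 | 16.6% | 0.8 points |
| 20% | 0.12389 | 15.7% | 1.7 points |

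The fall from 20% to 17.4% is the effect of competing death. It is a change of quantity, not an error: 17.4% is the actual incidence. Only the further fall is bias. On 37 patients it amounts to 0.008 × 37 = 0.3 to 0.017 × 37 = 0.6 of a patient.

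With a 15% risk in place of 20%, the same formula gives 13.0%, then 12.4% or 11.8%.

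**4. Later onset.** Suppose 20% of patients would develop pneumonitis at a time uniform over months 2 to 6. With h = d + c, the expected value is 0.20 × (exp(−2h) − exp(−6h)) / (4h). This gives 16.4%, then 15.3% or 14.2%, so the bias is 1.1 or 2.2 points.

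**5. Without the borrowed survival figure.** Set deaths aside and take a true 20%. If losses and onset are both uniform over 6 months, the crude value is 0.20 × (1 − L/2), or 19% and 18% at L = 10% and 20%. If every loss comes before any onset, it is 0.20 × (1 − L), or 18% and 16%. The bias is then 1 to 2 points, or 2 to 4 points in that extreme case.

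**The case against.** The strongest reply is that no section says patients who leave early are counted as free of pneumonitis. The sentence in section 11.0 contrasts assessability for toxicity with assessability for response, and it is not an imputation rule. An analyst might exclude such patients, which would raise the rate. It is true that this is not a written rule. But section 2.0 fixes the denominator as enrolled subjects and section 11.0 excludes nobody, so excluding patients would depart from both. If either choice is open, the primary result depends on an unwritten decision, and the same remedy applies.

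A second reply is that the bias is small: under one patient in 37 in the main illustration, and well inside the sampling error. That stands, and it limits how much weight the point can carry.

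A third is that the inputs are not the plan's. The 14-month median is a background result from an older chemotherapy-first trial in stage III disease. This trial enrols after chemoradiation, admits stage II and requires limited residual disease. That also stands. The figures are illustrations, and heavy early mortality in this population should not be assumed from them.

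A reader might also infer that early deaths make the boost look safer through bias. The documents do not support that. With follow-up to death, which section 8.2.1 provides for unless the patient withdraws, the crude proportion is a valid incidence in the presence of death. For the same reason, dividing by completers only would not be the right correction.

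**Conclusion.** The point holds in a limited form. The primary estimate has no rule for living patients whose toxicity assessment ends before month 6. Applied literally, it counts them as non-events and is biased downward. Under an assumed 10% to 20% loss, constant hazards and the borrowed 14-month median, the bias is roughly 1 to 2 points on an actual incidence of 17.4%, against a 90% half-width of about 11 points. If few patients are lost, it is negligible. Deaths add no bias, but they lower the rate, and the plan does not show them beside it. This is a worthwhile and inexpensive improvement to the primary safety estimate. It does not show that the trial would reach a wrong conclusion.

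**What to change.** In sections 2.0 and 10.1, define the primary estimate as the 6-month cumulative incidence of pneumonitis, counted from the first SBRT fraction, among patients who receive the boost. Use the Aalen-Johansen estimator with a 90% CI. Treat death without pneumonitis as a competing event. Censor living patients who have no 6-month evaluation at their last toxicity evaluation. Report the cumulative incidence of death without pneumonitis beside it. Keep the crude proportion of enrolled subjects as a secondary result, so that patients enrolled but not boosted remain visible.

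When every boosted patient is followed to pneumonitis, death or month 6, the new estimate equals the crude proportion among boosted patients, so nothing is lost. When some are not, it removes the downward bias, provided that loss is unrelated to pneumonitis risk.

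The costs are a change of wording, a slightly wider interval when patients are censored, and the recording of pneumonitis onset and last toxicity evaluation dates. The documents do not confirm that these dates are collected, so the case report form should be checked.
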